9.1.1. Sensitivity Analyses

Subjects with missing data will be treated as non-responders for efficacy analyses of responder rates. The following analyses will be performed to assess the impact of missing data:

- The primary efficacy analysis specified in [Section 9.1](#) will be repeated using:
 1. The Per-Protocol Set
 2. Study Completers.
 - Subjects who complete Week 16 treatment and have pertinent Week 16 efficacy data.

9.1.2. Subgroup Analyses

Subgroup analyses for the primary efficacy analysis specified in [Section 9.1](#) will be repeated using the following subgroups:

- Categorical Age
 - <55
 - ≥55
 - <65
 - ≥65
- Gender
 - Female
 - Male
- Race

- African American
- White
- Other (Asian, Native Hawaiian or Other Pacific Islander, American Indian or Alaska Native, Other)
- Categorical BMI
 - Underweight (<18.5)
 - Normal (18.5 - <25)
 - Overweight (25 - <30)
 - Obese (≥ 30)
- Type of MS
 - Relapsing remitting
 - Secondary progressive
 - Progressive with relapse
 - Progressive without relapse
- Time Since MS diagnosis
 - < Median of enrolled trial population
 - \geq Median of enrolled trial population
- EDSS Score at Baseline
 - 0 to 3.5 (No to minimal walking limitation)
 - 4 to 5.5 (Walking limitation)
 - 6 to 6.5 (Need for assistive device)
- Use of Assistive Devices During T25FW Test at Baseline
 - Yes / No
- History of Dalfampridine Use
 - Yes / No
- History of Amantadine Use
 - Yes / No
- T2FW Category at Baseline
 - < 26.5 seconds
 - ≥ 26.5 seconds

The results will be provided via summary tables and also presented graphically in a forest plot.

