5.1. Randomization, Stratification, and Blinding

A subject is considered randomized at Baseline/Week 4, when the site confirms the randomization event via a centralized randomization system (interactive web response system [IWRS]).

Following completion of the 4-week Single-Blind Placebo Run-in Period, consented subjects who continue to meet eligibility criteria will be randomly assigned in equal probability to 1 of 3 treatment groups: placebo, 137 mg ADS-5102, or 274 mg ADS 5102. No stratifications are being utilized in the randomization design.

The identity of the treatment assigned to individual subjects can be revealed in an emergency only. A subject's treatment assignment should only be unblinded when knowledge of treatment is essential for the safety of the subject. Emergency unblinding will be considered a major protocol deviation.

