5.2. Sample Size

Based on the results from the Phase 2 study, responder rates of 24% and 33% were observed at Week 4 for subjects treated with placebo and 274 mg ADS-5102, respectively, in the modified intent-to-treat (MITT) analysis set. In the present study, it is anticipated that the placebo response rate at Week 16 will be no greater than 20% and the response rate among subjects treated with 274 mg or 137 mg ADS-5102 will be at least 33%. Using these estimates, 180 randomized subjects per active treatment group and placebo group will be needed for the test of differences in proportions (Farrington-Manning approach for the Miettinen-Nurminen [MN] test) to have 80% power at the 2-sided 5% significance level to detect this 13% difference favoring ADS-5102. Assuming a 5% dropout rate during the 4-week Single-Blind Placebo Run-In Period, 570 subjects will be enrolled in the study to randomize 540.

For this sample size of 180 randomized subjects per group, power will be at least 80% to detect treatment differences (ADS-5102 versus placebo) of -2.7 seconds and 5.0 meters in the changes from baseline at Week 16 in the TUG test and 2MWT when the standard deviations of the

change from baseline are no greater than 6.0 sec and 14.9 meters, respectively, and the dropout rate is not greater than 20%.

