9.1. Primary Efficacy Analysis

The primary efficacy endpoint is the proportion of responders in each treatment group as defined in [Section 3.2.1](#).

The objective of the primary efficacy analysis is to compare the 274 mg ADS-5102 group versus the placebo group in terms of the difference (active minus placebo) in the proportion of responders at Week 16 using the ITT analysis set. The Farrington-Manning test will be used to obtain a 2-sided p-value based on the resulting Z-score. The Miettinen-Nurminen (MN) approach will be used to obtain the 95% confidence interval (CI) for the difference. Superiority will be concluded if the 2-sided p-value is less than 0.05 and the lower limit of the 2-sided 95% CI is greater than 0.00. (Note that this test is effectively a one-sided test at the 0.025 level.)

This test can be expressed mathematically as follows:

$$H_0: d = 0$$
$$H_1: d > 0$$

Where $d = p_1 - p_0$ (i.e. risk difference between the proportion of responders in the 274 mg ADS-5102 group and the proportion of responders in the placebo group).

The primary efficacy analysis will be provided via a summary table.

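### SAP 9.1.2 repeats the primary test in 30 subgroup levels but plans no test of whether the treatment effect differs between levels

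*Combined protocol and SAP*

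**What the plan says.** SAP 9.1.2 opens with "Subgroup analyses for the primary efficacy analysis specified in" Section 9.1, to be repeated over a list of subgroups. SAP 9.1 defines what is repeated: a Farrington-Manning two-sided p-value for 274 mg against placebo, a Miettinen-Nurminen 95% interval for the risk difference, and a decision rule. The rule begins "Superiority will be concluded if the 2-sided p-value is less than 0.05" and also requires the lower confidence limit to exceed zero.

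The list covers age (split at 55 and again at 65), gender, race, BMI, type of MS, time since diagnosis, EDSS, assistive device use, past dalfampridine, past amantadine, and baseline T25FW. Results go into summary tables and a forest plot.

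The only interaction in the SAP's models is treatment by study week, in the MMRM (SAP 9.2 and 12.1). Protocol Section 14 describes no subgroup analysis. For subgroups, neither document gives an exploratory label, a rule for sparse levels or a rule for reading the results. SAP 5.1 adds that "No stratifications are being utilized in the randomization design", so the balance of arms within a level is left to chance.

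**The concern.** A subgroup analysis asks whether the effect differs between levels. Repeating the primary test inside each level asks instead whether that level, taken alone, shows an effect. The answer depends on the effect in the level and, heavily, on how many subjects it holds. One level below 0.05 and its neighbour above it is not evidence that the effect differs.

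At stake is how the results are read. The tables will mix significant and non-significant levels whether or not the effect varies, and the plan offers no statistic that separates real variation from differences in level size. A reader could wrongly conclude that the drug works in one group and not in another.

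**Working it through.** **Inputs.** SAP 5.2 assumes 20% response on placebo and 33% on active. It says "180 randomized subjects per active treatment group and placebo group will be needed for the test of differences in proportions", with "80% power at the 2-sided 5% significance level to detect this 13% difference favoring ADS-5102". SAP 5.11 counts missing responses as non-response, so subjects without Week 16 data stay in the denominator. Subgroup shares are not in the documents and are assumed below.

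**Reproducing the plan's figure.** At a null difference of zero the Farrington-Manning Z is the pooled Z. The pooled rate is (0.20 + 0.33)/2 = 0.265.

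- Null SD term: √(2 × 0.265 × 0.735) = 0.624
- Alternative SD term: √(0.20 × 0.80 + 0.33 × 0.67) = √0.3811 = 0.617
- n = [(1.96 × 0.624 + 0.842 × 0.617)/0.13]² ≈ 180 per arm, with power 80.06%

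The stated 180 is confirmed.

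**Counting levels.** Age 4, gender 2, race 3, BMI 4, MS type 4, time since diagnosis 2, EDSS 3, device 2, dalfampridine 2, amantadine 2, T25FW 2: total 30. Age forms two partitions, so there are 12: eight with two levels, two with three and two with four.

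**Power within a level.** With m subjects per arm and the same 20% vs 33% in every level, power = Φ[(0.13√m − 1.96 × 0.624)/0.617].

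| Share of each arm | m | Power | 95% CI half-width | Chance estimate ≤ 0 |
|---|---|---|---|---|
| 5% | 9 | 9% | 40 points | 26% |
| 10% | 18 | 14% | 29 points | 19% |
| 25% | 45 | 28% | 18 points | 8% |
| 33% | 60 | 36% | 16 points | 5% |
| 50% | 90 | 51% | 13 points | 2% |
| 90% | 162 | 76% | 10 points | 0.4% |

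The half-size row is not hypothetical: time since diagnosis is cut at the median. The chance that exactly one of two equal halves reaches p<0.05, with identical effects in both, is 2 × 0.506 × 0.494 = 0.50.

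**Expected misses under a uniform effect.** With even splits the expected number of levels reaching p<0.05 is 16 × 0.506 + 6 × 0.363 + 8 × 0.285 ≈ 12.6, so 30 − 12.6 = 17.4 miss. A grid search over unequal splits found none that raised the 12.6, so 17.4 is about the minimum whatever the level sizes. An illustrative skewed set, with shares from 3% to 90%, gives 18.0.

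**Spread.** I simulated 4,000 trials per scenario, with membership independent across factors. Ranges are over the even and skewed splits.

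| True effect | Mean misses of 30 | Chance that more than 15 miss |
|---|---|---|
| 20% vs 33% | 17.5 to 17.9 | about 60% |
| Same, given primary success | 15.1 to 15.6 | about 50% |
| 20% vs 40% | 8.0 to 10.7 | about 13% |

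At 20% vs 33%, only about 1.4 to 2.6 of the 30 estimates fall at or below zero (0.6 to 2.0 given primary success).

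**No effect anywhere.** The rule needs the lower limit above zero, so each level has about a 2.5% chance of falsely favouring the drug: 30 × 0.025 = 0.75 levels. (30 × 0.05 = 1.5 would count both directions.) The simulated chance of at least one such level is 32% to 33%.

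**What a heterogeneity test would offer.** For two equal halves, the SE of the difference of differences is √(0.3811/90 + 0.3811/90) = 0.092.

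- Power for a 13-point difference: Φ(0.13/0.092 − 1.96) ≈ 29%
- Power for a 26-point difference: about 81%
- For a 90/10 split: about 13% and 40%
- Under a uniform effect, 12 tests at 5% give 12 × 0.05 = 0.6 expected flags, and 1 − 0.95¹² = 46% chance of at least one if independent

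**The case against.** The strongest reply is that the plan already supplies most of what a careful reader needs. Repeating Section 9.1 yields a risk difference and Miettinen-Nurminen interval per level, and a forest plot is promised. If the plot shows those estimates and intervals, a reader will see consistent direction with wide intervals. No subgroup appears in the fixed sequence of SAP 9.2, and no passage says that efficacy will be judged from a within-level p-value. The superiority rule is written for 274 mg against placebo in the ITT set. The proposed tests are also weak and can raise false flags.

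All of this stands, and it limits the consequence. It rules out two stronger readings that a reader might infer:

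- **That most subgroups will look ineffective.** Missing p<0.05 here mainly reflects wide intervals, since nearly all estimates would still favour the drug. A majority of misses is an expectation, not a certainty: it occurs in about 60% of trials at the design effect, about 50% once the primary test has succeeded, and far fewer if the effect is larger.
- **That the SAP plans subgroup claims or inflates the trial's type I error.** It does neither.

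The reply does not answer the remaining gap. Intervals and a forest plot are not a test of whether levels differ, and the literal text still carries a p-value and superiority rule into each level. SAP 9.2 says that significant results after a failed step are supportive only; SAP 9.1.2 has no comparable sentence.

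**Conclusion.** The point holds as a weakness of reporting and interpretation. SAP 9.1.2 plans 30 within-level tests and no test of effect modification. At the design effect, about 17 to 18 of 30 levels are expected to miss p<0.05 even when the effect is identical everywhere, so the pattern of significant and non-significant levels says little about where the drug works.

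The within-level powers assume 20% vs 33% in every level, balanced arms within levels, and a normal approximation that is rough for the smallest levels. The lower figure of about 17.4 does not depend on the unknown level sizes. The 18.0 rests on assumed shares, and the simulated spread on independence between factors. The primary result and the key secondary sequence stand as planned.

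**What to change.** Amend SAP 9.1.2 as follows.

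1. Keep the risk difference and Miettinen-Nurminen 95% interval for every level, in the tables and the forest plot.
2. Drop the within-level p-values.
3. State that the Section 9.1 superiority rule is not applied within subgroups and that these analyses are exploratory.
4. For each of the 12 partitions, add one treatment-by-factor heterogeneity test on the risk-difference scale. With level estimates d_k and weights w_k = 1/SE_k², refer Σ w_k(d_k − d̄)² to chi-square with (levels − 1) degrees of freedom, where d̄ is the weighted mean. For two levels, report the difference of differences with its 95% interval.

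I would not add a general rule that pools levels below a fixed share such as 10%. Race and MS type have no natural neighbour to pool with, and a two-level factor with a rare level would disappear. A level at exactly 10% has about 14% power in any case. Instead, say in advance, factor by factor, what happens when a level is too sparse for the statistic to be computed.

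The cost is a few lines of SAP text and 12 exploratory p-values in place of 30. Data collection, sample size and the primary analysis do not change. The downside is the low power and the false-flag rate shown above: a non-significant heterogeneity test does not establish a uniform effect, and a single flag among 12 is weak evidence. The SAP should say both.

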9.2. Key Secondary Efficacy Analyses

The key secondary endpoints are the mean changes from Baseline between treatment groups at Week 16 for the T25FW (feet/second), TUG (s), and 2MWT (m). These are described in [Section 3.2.2.1](#).

Provided superiority of 274 mg ADS-5102 versus placebo is shown in the primary analysis, the key secondary objectives will be evaluated using a fixed-sequence gatekeeping strategy to control the overall Type I error rate at 5%. Using this approach, the following research hypotheses will be evaluated sequentially in the order given using the ITT analysis set:

1. Superiority of 274mg ADS-5102 compared to placebo in mean change from baseline at Week 16 in the T25FW(feet/second) test

2. Superiority of 274 mg ADS-5102 compared to placebo in mean change from baseline at Week 16 in the TUG (s) test
3. Superiority of 274 mg ADS-5102 compared to placebo in mean change from baseline at Week 16 in the 2MWT (m)
4. Superiority of 137 mg ADS-5102 compared to placebo in terms of the proportion of T25FW responders at Week 16
5. Superiority of 137 mg ADS-5102 compared to placebo in mean change from baseline at Week 16 in the T25FW (feet/second) test
6. Superiority of 137 mg ADS-5102 (s) compared to placebo in mean change from baseline at Week 16 in the TUG test
7. Superiority of 137 mg ADS-5102 compared to placebo in mean change from baseline at Week 16 in the 2MWT(m)

At each step, superiority will be concluded if the 2-sided p-value is less than 0.05 and the lower limit of the 2-sided 95% CI is greater than 0.00, for tests comparing responder rates or mean changes from baseline in 2MWT and T25FW, or the 2-sided 95% CI is less than 0.00, for tests comparing mean changes from baseline in the TUG. If a non-significant result (p-value ≥ 0.05) or a p-value < 0.05 is noted but superiority is not shown, no further inferential conclusions will be drawn and any subsequent statistically significant result will be declared supportive of efficacy only. This strategy effectively controls the Type I error rate at the 2.5% level (one-sided) for testing superiority of ADS-5102 versus placebo.

The statistical test of difference between 137 mg ADS-5102 versus placebo in terms of responders at Week 16 (Item 4 above) will be done using the same approach used for the primary analysis.

The hypothesis tests of difference between 274 mg ADS-5102 and of 137 mg ADS-5102 versus placebo in terms of the mean change from baseline in the T25FW, TUG test, and the 2MWT, as described above, will be done using t-tests derived from the corresponding linear mixed model with repeated measurement (MMRM) model with the change from baseline (i.e., T25FW, TUG, or 2MWT) as the dependent variable and fixed effects of treatment group, study week, and treatment by study week interaction. The baseline value will be included as a covariate and an unstructured variance-covariance matrix will be used for the within-subject residual variability. Should the model fail to converge under this assumption, then a compound symmetry covariance structure will be assumed. The Kenward-Rogers method will be used to estimate the denominator degrees of freedom.

All key secondary analyses will be repeated using the PP set.

Least squared mean change from baseline values will be presented graphically by visit and treatment for the T25FW, TUG, and 2MWT.

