3.2.2. Secondary

3.2.2.1. Key

The key secondary endpoints listed below will be used for comparisons between treatment groups for which inferential statistics, with appropriate control of the Type I error rate, will be used.

- The mean change from baseline at Week 16 in the T25FW (feet/second)
- The mean change from baseline at Week 16 in the TUG (s)
- The mean change from baseline at Week 16 in the 2MWT (m)

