3.2.2.2. Supportive

The following endpoints will be used for supportive comparisons among treatment groups.

- Mean changes from baseline in the T25FW (feet/second) at Weeks 8 and 12
- Mean changes from baseline in the T25FW (s) at Weeks 8, 12 and 16
- Mean changes from baseline in the TUG (s) at Weeks 8 and 12
- Mean changes from baseline in the 2MWT (m) at Weeks 8 and 12

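### If triggered, the SAP's only covariance fallback (homogeneous compound symmetry with model-based inference) misstates the Week 16 standard error unless Week 16 variance is close to the average over visits

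*Combined protocol and SAP*

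**What the plan says.** SAP 9.2 tests the Week 16 mean changes in T25FW speed, TUG and 2MWT with one repeated-measures model per endpoint. Each has "fixed effects of treatment group, study week, and treatment by study week interaction", with baseline as a covariate. The starting covariance is clear: "an unstructured variance-covariance matrix will be used for the within-subject residual variability". The fallback follows at once: "Should the model fail to converge under this assumption, then a compound symmetry covariance structure will be assumed". Inference is model-based: "The Kenward-Rogers method will be used to estimate the denominator degrees of freedom". No sandwich variance is mentioned.

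Protocol 14.4.2 names only the unstructured matrix and has no fallback, so this SAP sentence governs alone. The two multiple-imputation analyses in SAP 9.2.1 vary the missing-data assumption, not the covariance structure.

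These models supply hypotheses 1–3 and 5–7 of the fixed sequence in SAP 9.2. Of that sequence the SAP says: "This strategy effectively controls the Type I error rate at the 2.5% level (one-sided". The same model also serves the supportive analyses (SAP 9.3) and the percent-change analysis (SAP 12.1).

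**The concern.** Compound symmetry imposes one variance on Weeks 8, 12 and 16 and one correlation on every pair of visits. The hypotheses concern Week 16 only. When the visits differ in variance, the fitted common variance is roughly their average, and the Week 16 standard error inherits it. The Kenward-Roger method adjusts degrees of freedom and small-sample precision given the assumed structure; it does not repair a wrong structure.

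In a fixed sequence, a standard error that is too small can wrongly open later tests, and one that is too large can wrongly close them. The fallback also passes over structures that are simpler than unstructured yet keep a separate Week 16 variance. With three visits the parameter counts are: unstructured 6, heterogeneous Toeplitz 5, heterogeneous AR(1) 4, heterogeneous compound symmetry 4, homogeneous compound symmetry 2.

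**Working it through.** **Inputs from the documents.**
- Post-baseline visits in the model: Weeks 8, 12 and 16 (SAP 3.2.2.2, for example "Mean changes from baseline in the T25FW (s) at Weeks 8, 12 and 16").
- 180 randomized per arm; 2MWT effect 5.0 m and SD of Week 16 change at most 14.9 m; TUG effect -2.7 s and SD at most 6.0 s; dropout at most 20%; responder rates 20% and 33% (SAP 5.2).

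**Assumptions.** The documents give an SD only for the Week 16 change. The visit-to-visit variance patterns, the correlations and the timing of dropout below are therefore assumed.

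**The plan's own figures reproduce.**
- Responder test, 20% vs 33%, two-sided 5%: 180 per arm, power 80.1%.
- Run-in: 540/0.95 = 569, stated as 570.
- At 180 × 0.8 = 144 evaluable per arm, power is 96.8% for TUG and 81.3% for 2MWT, so the stated minimum of 80% holds.

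**Complete data.** Let v8, v12 and v16 be the residual variances. The true Week 16 standard error is √(2·v16/n). Compound symmetry reports √(2·v̄/n), with v̄ = (v8 + v12 + v16)/3. So

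- ratio of reported to true SE = √(v̄/v16);
- two-sided type I error = 2·[1 − Φ(1.96 × ratio)].

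| Assumed variances, Weeks 8:12:16 | v̄ | √(v̄/v16) | Type I error |
|---|---|---|---|
| 1 : 1.1 : 1.2 | 1.100 | √(1.100/1.2) = 0.957 | 6.1% |
| 1 : 1.2 : 1.5 | 1.233 | √(1.233/1.5) = 0.907 | 7.6% |
| 1 : 1.5 : 2.0 | 1.500 | √(1.500/2.0) = 0.866 | 9.0% |
| 1.5625 : 1.21 : 1 (SDs 1.25/1.1/1) | 1.2575 | √1.2575 = 1.121 | 2.8% |

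In 2MWT units the true standard error is 14.9 × √(2/180) = 1.571 m. With relative SDs 0.8/0.9/1, v̄ = (0.64 + 0.81 + 1)/3 = 0.817, and the reported value is 1.571 × √0.817 = 1.419 m.

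**With 20% dropout.** Assumed: 10% lost after Week 8 and 10% after Week 12, completely at random, with AR(1) correlation 0.7. The ratio and type I error are large-sample values. The last two columns are null rejection rates from 1,000 simulated three-arm trials of 540 subjects per pattern (Monte Carlo SE about 0.7 points). The simulations used maximum-likelihood fits rescaled for degrees of freedom, not SAS Kenward-Roger; at this size the difference is negligible.

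| Relative SDs, Weeks 8/12/16 | Ratio | Type I error | Simulated, compound symmetry | Simulated, unstructured |
|---|---|---|---|---|
| 1/1/1 | 0.987 | 5.3% | 5.7% | 5.3% |
| 0.9/0.95/1 | 0.935 | 6.7% | not run | not run |
| 0.8/0.9/1 | 0.884 | 8.3% | 8.0% | 5.1% |
| 0.6/0.8/1 | 0.790 | 12.1% | 11.9% | 5.3% |
| 1.25/1.1/1 | 1.114 | 2.9% | 3.1% | 5.0% |

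**Power when variance falls (2MWT, last row).** Compound symmetry reports 1.902 m against a true 1.708 m, so power is Φ[(5.0 − 1.96 × 1.902)/1.708] = Φ(0.745) = 77%. Unstructured, with SE 1.688 m, gives Φ(5.0/1.688 − 1.96) = Φ(1.002) = 84%.

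**How likely is the trigger?** Six covariance parameters are estimated from about 540 subjects. The unstructured estimate was positive definite in all 4,000 simulated trials.

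**The case against.** The strongest reply is that the rule will almost certainly never be used. With three visits and about 540 subjects an unstructured fit should converge, so the error rates above are conditional on a rare event and the unconditional effect is close to nil. That stands, and it limits the weight of the point.

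The design also gives some reason to expect only modest differences in variance. All three visits fall in the maintenance phase, after titration ends at Week 6 (protocol 9.4), and they span eight weeks. Protocol 5.6 regards the drug as symptomatic and expects the run-in to reduce practice effects on variability. None of this establishes equal variances, but rising variance is an assumption too, and a doubling from Week 8 to Week 16 is only illustrative.

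A reader might infer four stronger things that the documents do not support:
- *The standard error is wrong whenever variance changes over time.* It is right with complete data if Week 16 variance equals the average. Relative SDs 1.1/0.889/1 give (1.21 + 0.790 + 1)/3 = 1.000 and a ratio of 1; with 20% dropout the ratio stays within about 1%.
- *All six tests are compromised.* There is a separate model for each endpoint. One failure affects two tests, one per dose; all six are affected only if all three models fail.
- *The sequence does not control type I error.* That needs both non-convergence and above-average Week 16 variance. The primary test uses no repeated-measures model and gates the sequence, so error under the global null remains bounded by it.
- *Compound symmetry is the most restrictive choice available.* Independence has one parameter, and homogeneous AR(1) has the same two.

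What survives is the conditional defect: where the fallback is used, it does not protect the Week 16 inference.

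**Conclusion.** The point holds in conditional form. If an endpoint's unstructured model fails, the SAP's rule gives a Week 16 standard error based on roughly the three-visit average variance. With complete data and the assumed rising variances, two-sided type I error for that test is about 6% to 9%. With the assumed falling variances it is about 3%, and with 20% dropout 2MWT power is 77% instead of 84%. The direction and size in this trial cannot be known from the documents. The dropout calculations assume loss completely at random, so they speak to the standard error and not to bias in the estimate.

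The scope is two gatekept tests per failing model, plus the supportive and percent-change analyses that share the method. The primary responder test and hypothesis 4 are unaffected. This is a specification gap with a low chance of mattering. It is worth closing because a prespecified fallback exists for exactly the rare case in which this one performs poorly.

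**What to change.** Replace the fallback sentence in SAP 9.2 with an ordered rule, applied to each endpoint separately:

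1. Unstructured, as now.
2. If it does not converge, heterogeneous Toeplitz, then heterogeneous AR(1), then heterogeneous compound symmetry. Take the first that converges, with Kenward-Roger. The Toeplitz step saves only one parameter over unstructured, so the later steps are needed.
3. If all fail, one named last resort: either a simpler structure with a robust (sandwich) standard error and a compatible degrees-of-freedom method, or a Week 16 ANCOVA on multiply imputed data. If ANCOVA is chosen, specify the MAR imputation of SAP 9.2.1. The placebo-based NMAR imputation would change the missing-data assumption of a confirmatory test.
4. Do not use homogeneous compound symmetry with model-based standard errors.

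The cost is slightly longer SAP text and some programming, used only if the unstructured model fails. No new data are needed, and no result changes if that model converges.
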